3.5 Study Timeline

Primary Completion:

- The study will reach primary completion 48 months from the time the study opens to accrual.

Study Completion:

- The study will reach study completion 72 months from the time the study opens to accrual.

4. TREATMENT PLAN

Pre-op procedure:

- LSG baseline (it may be the same as one performed for research purposes)
- Venous duplex to evaluate the superficial and deep venous systems for clots and valvular insufficiency
- ICG fluorescence lymphatic mapping to assess the superficial lymphatic system
- Labs: CBC, CMP, PT/PTT, EKG, CXR
- Research samples: blood and skin samples; optional for control group
- Baseline photograph of limbs

Post-op:

- LSG at 12 months (it may be the same as one performed for research purposes)
- ICG fluorescence lymphatic mapping at 12 months

- Research samples: blood and skin samples; skin biopsies are optional for control group
- Photograph at 12 months

Time of procedure:

Operating time ~6 hours, additional 45 min for BioBridge placement; anesthesia ~10 to 12 hours, positioning, IV and arterial line placement, OR, etc (time is variable).

Description of procedure:

On the day of surgery, the patient will be sent to radiology for injection of Technecium-99 in the second web space of bilateral feet or contralateral arm in preparation for intraoperative lymph node transfer. Patient will be marked in the preoperative area. Patient will then be taken to the operating room, placed on the operating room table in the supine position with both arms abducted. Perioperative antibiotic will be given on-call to the OR. After general endotracheal anesthesia is established, the entire anterior chest, abdomen, proximal thighs and arm(s) will be prepped and draped in the usual sterile fashion. A surgical pause is taken to identify the patient and the procedure(s) to be performed.

Attention will be turned to the left or right groin lymph node region or right or left neck for supraclavicular lymph node region. A Doppler is used to confirm the location of the lymph node pedicles. Next, reverse lymphatic mapping is used as an additional method to confirm the location of the lymph nodes. Technecium-99 will be injected preoperatively into the foot or hand (depending on donor site). A gamma probe is used to localize the sentinel lymph node draining the extremity, which will be avoided during flap harvest. The highest gamma probe count is noted and the donor site is deemed suitable only if the gamma probe count for the planned lymph node donor site is <10% of the previously noted maximum. Indocyanine green (ICG) 0.2 mL is injected intraoperatively into several sites along the periphery of the donor flap (lower abdomen or supraclavicular) for lymphatic mapping. Fluorescence angiography is used to visualize the lymph nodes draining the lower abdominal wall or supraclavicular region.

Groin donor flap:

The lymph nodes draining the lower abdomen are visualized and correlated with the SCIA-based lymph nodes. An incision is made into the lower (left or right) abdomen and the skin flaps are elevated just above the Scarpa fascia. At the superior edge of the flap, the SCIV and SIEV are both identified and divided, with the knowledge that most of the target lymph nodes will lay between these vessels. The flap will be elevated lateral to medial just above the sartorius fascia. The SCIA branch to the Sartorius muscle is divided, and the SCIA and branches of the SCIV are mobilized to their origin and are harvested for transfer.

The groin wound is irrigated with an antibiotic solution and hemostasis is achieved. The inguinal fascia, if needed, may be reinforced with an onlay polypropylene mesh, secured with interrupted and running 2-0 Prolene sutures. A Blake drain will be placed to drain the groin

wound. The wound is closed with interrupted 2-0 Vicryl sutures for the Scarpa, interrupted 3-0 Vicryl sutures for the dermis and 4-0 Monocryl running subcuticular stitch.

Supraclavicular donor flap:

A transverse incision, 1 cm above the clavicle in the posterior neck triangle, will be made. The superior skin flap will be elevated in the subplatysmal plane using a bovie. Dissection will proceed medial to lateral to include all the intervening subcutaneous tissues and lymph nodes in the posterior triangle below the omohyoid muscle. The transverse cervical artery and vein will be identified. Once the flap is islandized on its pedicle, a handheld Doppler is used to confirm perfusion in the lymph node flap.

The pedicle to flap will be ligated and clipped. The donor site is irrigated and hemostasis confirmed. A Blake drain will be placed in the wound, and secured to the skin with Nylon suture. The platysma is reapproximated with 3-0 Vicryl sutures, and the wound will be closed with interrupted 3-0 Vicryl sutures for the dermis and 4-0 Monocryl running subcuticular stitch. The incision is cleaned and dressed with dermabond, Telfa and a sterile pressure dressing.

Next, the recipient vessels are dissected in the upper arm. A curvilinear incision will be made in the medial posterior aspect of the arm above the elbow crease. The skin flaps are elevated off the underlying structures using a bovie to create a pocket for the fascial-lymph node flap. Small superficial veins are identified and dissected free. The basilic vein and medial cutaneous nerve of the arm are identified and preserved. The superior or inferior recurrent ulnar artery is identified, and dissected distally to gain pedicle length. The lymph node dermal fat flap is then harvested; the SCIA and SCIVs are anastomosed to the distal end of the superior or inferior recurrent ulnar artery and its vena commitantes using interrupted 10-0 or 11-0 nylon sutures for the arterial anastomosis and venous couplers.

SutureEase device will be used to tunnel five 15 cm long Fibralign BioBridge Collagen Matrix individually in the subcutaneous tissue from the lymph node flap down to the mid forearm. 3 additional 15 cm long BioBridge Collagen Matrix are similarly tunneled proximally pass the shoulder toward the neck and two 15 cm long BioBridge Collagen Matrix are tunneled to the axilla. Prior to implantation, the BioBridge is moistened in saline, to facilitate gliding in tissue. Once this is completed, the skin flaps are redraped over the fascial-lymph node flap and closed with interrupted 3-0 Vicryl sutures for the dermis and 4-0 Monocryl running subcuticular stitch for the skin. The total length of time spent on placement of the Biobridges is about 45 minutes.

At the end of the procedure, Doppler signal from the flap, correct sponge and needle counts will be verified. Minimal blood loss is expected. The patient will be awakened; extubated; and transferred to the recovery room.

Standard PACU recovery: 1 to 1.5 hrs.

Hospitalization: 2 to 3 days, managed postoperative in accordance to the institution standardized free flap protocol.

Post-op instructions (specific to this procedure-VLNT): patients are instructed to keep their surgical arm elevated x 3 weeks at level of heart or above. Otherwise, patient may ambulate, eat and resume normal light activities that does not require use of treated arm. Patients will be instructed to not wear compression garments for 3 weeks post-operative.

Participants will be given consent form and contact information to take home for their consideration. Samples (skin punch biopsy and blood) may be retained for future research use if patient has given consent (in ICF). Pre-treatment and post-treatment photographs will be taken.

Study Visits

There are 3 screening visits.

S1: after obtaining written consent, medical history, symptoms, current medications, and allergies will be reviewed, height/weight/VS, physical exam by PI will be conducted, limb measurements performed (volume, BIS, caliper), and LymQoL survey completed.

S2: VS, weight, medication and allergy review, measurements; if measurements are consistent, will proceed to skin punch biopsy (optional for control group); research labs will be drawn. No compression garment wear x 10 days.

S3: VS, weight, medication and allergy review, measurements, stitch removal, LSG. Patients resume wearing compression; after 3 weeks, eligible to proceed with surgery.

VLNT, 2 groups; one with BioBridge scaffold (intervention group), one VLNT only (control group), will occur between S3 and T1 visits.

T1 (3 months following surgery): physical exam, measurements, LymQoL survey, medication and symptom/AE review, VS, weight.

T2 (6 months following surgery): physical exam, measurements, LymQoL survey, medication and symptom/AE review, VS, weight

T3 (9 months following surgery): physical exam, measurements, LymQoL survey, medication and symptom/AE review, VS, weight.

T4 (12 months following surgery): physical exam, measurements, LymQoL survey, medication and symptom/AE review, VS, weight, skin punch biopsy (optional for control group), research labs. No compression garment wear x 10 days.

T5 (10 days after T4 visit): measurements, LymQoL survey, medication and symptom/AE review, VS, weight, stitch removal, LSG

T6 (2 years following surgery, BioBridge participants/intervention group): physical exam, medication and symptom/AE review, VS, weight.

T7 (3 years following surgery, BioBridge participants/intervention group): physical exam, medication and symptom/AE review, VS, weight.

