2.4 Study Design

For clinicaltrials.gov and Stanford Clinical Trials Directory compliance

- Primary purpose of the protocol:
 - **Treatment:** protocol designed to evaluate one or more interventions for treating a disease, syndrome or condition
- Interventional model:
 - **Parallel:** one of two groups in parallel for duration of study.
- State the number of intervention arms
 - **Two arms**
- State whether the study will be masked (at least one party is unaware of the treatment)
 - **Open:** no masking is used
- State whether the study is randomized.
 - **Randomized**
- Primary outcome or outcome that the protocol is designed to evaluate:
 - **Efficacy**

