4.3 Alternatives

Alternatives to participation in this trial include enrollment in VLNT without the addition of the BioBridge scaffold or standard of care treatments for lymphedema. These include, but are not limited to, compression sleeves or compression devices, decongestive therapy, intermittent pneumatic compression devices. In general, there are 4 types of surgical intervention for lymphedema, as follows.^{35,36,46-48}

Lymphatic Microsurgical Preventive Healing Approach (LYMPHA), aimed at lymphedema prevention, was developed at the University of Genoa.^{37,38} At the time of axillary lymph node dissection, a lymphaticovenous anastomosis (LVA) is performed to restore lymphatic flow. While a comparatively new procedure, for patients undergoing ALND, results have been very promising.³⁹ However, since it is aimed at lymphedema prevention, LYMPHA is not an appropriate alternative for this participant population, since inclusion into this trial requires a diagnosis of lymphedema.

Excisional surgery, suction-assisted protein lipectomy (SAPL), pioneered by [name], is performed for chronic non-pitting lymphedema. SAPL is highly effective at removing the excess solid tissue (hypertrophied adipose tissue) but does not restore lymphatic function. [name], who trained with [name], frequently performs this procedure. Post-operatively, the continuous use (24 hours/day, 7 days/week) of custom compression garments is required. These may need to be frequently replaced in the 1st year after the procedure. Maintenance of reduction is dependent on patient compliance with continuous compression garment use.⁴⁰ SAPL is also not an appropriate alternative, since its aim is removal of excess tissue and not the restoration of lymphatic function.

Microvascular reconstruction with LVA is also performed by [name]. A large study, by Chang, *et al*, noted that LVA, is most effective in early stage lymphedema of the upper extremity. Early volume reduction may be seen in the first postoperative week but maintenance of response is unknown due to short follow-up.⁴¹ Additionally, LVA may not enhance the regional immune impairment that accompanies lymphedema.

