9. STUDY CALENDAR

	Pre-Study	S1	S2	S3	Surgery: VLNT with BioBridge (BB) Or VLNT only	T1 Mo. 3	T2 Mo. 6	T3 Mo. 9	T4 Mo. 12	T5 D-10 FU	T6 2-yr FU (BB group Only)	T7 3-yr FU (BB group Only)
Investigational Device (BioBridge Matrix)					X	X	X	X	X	X	X	X
Informed consent	X											
Demographics	X											
Medical history	X											
Concurrent meds	X	X	X	X		X	X	X	X	X	X	X
Physical exam	X	X		X		X	X	X	X	X	X	X
Vital signs	X	X	X	X		X	X	X	X	X	X	X
Height	X											
Weight	X	X	X	X		X	X	X	X	X	X	X
Performance status (ECOG)	X	X				X	X	X	X	X	X	X
CBC w/diff, platelets	X											
Serum chemistry	X											
EKG (as indicated)	X											
Adverse event evaluation		X	X	X		X	X	X	X	X	X	X
Measurements (BIS, VM, calipers)		X	X	X		X	X	X	X	X		
LymQoL survey		X	X			X	X	X	X	X		
Skin punch biopsy (optional for control group)			X						X			
Research labs			X						X			
Radiologic evaluation (Lymphoscintigraphy)				X						X *		
Pregnancy test (as indicated)												

* BioBridge Matrix recipients only.

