12.4 Primary Analysis

Limb circumference of the affected and unaffected limbs of each participant will be measured for calculation of the volume of the arm through the truncated cone formula.²³ Circumferential measurements of each limb will be obtained with a low stretch gauged tape measure applied at specified intervals of 4 cm (starting from the 3rd metacarpal head) along the axis of the arm, beginning at the wrist. Anatomic landmarks are recorded to facilitate reproducibility between pre- and post-surgical measurements. This method is inexpensive, reproducible, and easily applied. These measurements will be performed at initial evaluation and at each scheduled follow-up visit. The pre-surgical baseline volume for each limb will be defined as the average of the two measurements obtained on study day S1 and study day S2. For quantitative analysis, the excess volume of the limb is defined as the arithmetical difference between the affected

limb (L_{pre}) and the contralateral normal limb (C_{pre}) and the % excess volume at the beginning of the study is defined by:

$$100\% * [(L_{pre} - C_{pre})/C_{pre}].$$

The primary outcome is defined the post-surgical % change in excess limb volume:

$$100 * \{1 - [(L_{post} - C_{post})/(L_{pre} - C_{pre})]\}$$

Analysis Population

Participants are randomized into 1 of 2 arms, the intervention arm (VLNT with BioBridge) or control arm (VLNT-only). The primary analysis will include all participants who have completed all required study visits. However, for participants who do not complete the study, their data will be censored and analyzed with the current population. Treatment summary and adverse event data will also be provided for each treatment category separately.

Efficacy and safety analyses will be performed on all participants who have undergone VLNT (with or without BioBridge). The primary analysis will include all participants who have completed all required study visits and procedures. However participants who do not complete the study will be censored and their data will be analyzed, along with ongoing participants. Data including adverse event data will be captured for each treatment category separately.

Analysis Plan

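### The time of randomization is not stated, but the S2 biopsy rule requires the arm to be known at least 31 days before surgery, so withdrawal before surgery can depend on the arm

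*Combined protocol and SAP*

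**What the plan says.** **Randomization.** Sections 3.4 and 12.1.1 give the 4:1 ratio, and Section 3.4 adds the block size of 5 and how the block order is generated. Neither places randomization in the visit sequence. Section 2.4 records that "no masking is used".

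**Visits before surgery (Section 4, Study Visits).**
- At S2 the measurements come first; then, "if measurements are consistent, will proceed to skin punch biopsy (optional for control group".
- S2 closes with the instruction "No compression garment wear x 10 days".
- The next visit reads "S3: VS, weight, medication and allergy review, measurements, stitch removal, LSG", followed by "Patients resume wearing compression; after 3 weeks, eligible to proceed with surgery".

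The Section 9 calendar agrees. The row "Skin punch biopsy (optional for control group" is marked at S2 and T4 and not at S3.

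**Baseline and eligibility.** Section 12.4 takes baseline volume as the mean of S1 and S2. Section 10.1.2 refers to the two qualifying screening visits. Criterion 3.1.12 requires two consecutive volumes within 10% of each other, with at most three measurements.

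**Blinding.** It is stated for the caliper assessor (10.2.3), the reviewer of the volume results (10.1.5) and the lymphoscintigraphy reader (10.3.2.5). It is not stated for the person who takes the tape measurements.

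**Alternatives (Section 4.3).** "Alternatives to participation in this trial include enrollment in VLNT without the addition of the BioBridge scaffold".

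**Analysis set (Section 12.4).** One paragraph says "Efficacy and safety analyses will be performed on all participants who have undergone VLNT (with or without BioBridge", and limits the primary analysis to those who completed all required visits. The Analysis Plan in the same section instead takes everyone enrolled and assigned, by planned treatment, but a participant lost to follow-up enters the model only with at least one post-baseline value.

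**The concern.** If the arm is open at S2, each participant knows it through the compression-free period, the S3 visit and the weeks before surgery. A control then knows that the trial offers an operation that Section 4.3 says can be had without it. Leaving at that stage can be related to the arm and also to prognosis.

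Randomization protects the comparison only if those randomized are followed and analysed. With 12 controls, one or two selective departures change the control group noticeably, and the plan makes no allowance for them: 60 are randomized (12.1.1) and 60 completers are assumed (12.6.2).

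A second, conditional risk concerns the baseline. If the arm is opened before the S2 tape measurements, the denominator of the primary endpoint and the 10% check could both be influenced by knowing it.

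**Working it through.** **1. When must the arm be known?** The biopsy follows the S2 measurements, and its stitches come out at S3, so it is done at or just after S2. Whether it is optional depends on being a control. The arm must therefore be known by the S2 biopsy, though not necessarily by the S2 measurements.

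**2. Length of the window.** S2 to S3 is 10 days, taking S3 at the end of the compression-free period. S3 to the earliest surgery is 3 weeks, or 21 days. So 10 + 21 = 31 days at least.

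**3. What happens in the analysis to someone who leaves in the window?**
- Set of those who underwent VLNT: excluded, because there was no surgery.
- Set of those completing all visits: excluded.
- Set of all assigned, by planned treatment: nominally included, but the model needs a post-baseline value and the first is T1, 3 months after surgery. Normally excluded in practice.
- Multiple-imputation sensitivity analysis: could bring leavers back, but its departure from missing at random is specified only for missing values in the treatment arm. Selective loss of controls is not stress-tested.

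**4. The plan's own power figure.** Inputs from 12.6.2 and 12.6.3: SD 19, difference 20 points, 48 v 12, alpha 0.05, power 0.90. Two-sided, following the alternative in 12.4.
- SE = 19 × √(1/12 + 1/48) = 6.13.
- Detectable difference = (1.960 + 1.282) × 6.13 = 19.9 points, which reproduces the stated 20.
- Power at 20 points: 0.903 by normal approximation; 0.894 by noncentral t (noncentrality 20/6.13 = 3.26, 58 df).

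**5. Illustrative loss of controls.** Assumption: all 48 intervention participants stay. Noncentral t throughout.

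| Controls left | SE | Noncentrality | Power |
|---|---|---|---|
| 12 | 6.13 | 3.26 | 0.894 |
| 11 | 6.35 | 3.15 | 0.872 |
| 10 | 6.60 | 3.03 | 0.845 |
| 9 | 6.90 | 2.90 | 0.812 |

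**6. Illustrative selection bias.** Suppose k of the 12 controls leave and their mean lies D standard deviations from the mean of all 12. The mean of those who stay then moves by k/(12 − k) × D × 19 points, in the opposite direction. With D assumed at 0.5 to 1:
- k = 1: 0.9 to 1.7 points
- k = 2: 1.9 to 3.8 points
- k = 3: 3.2 to 6.3 points

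The target difference is 20 points. The documents do not indicate the direction.

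**7. Baseline volume, only if the arm is opened before the S2 measurements.** Assume a true excess of 20% of the unaffected limb (the eligibility floor in 3.1.12) and a true reduction of 51% (12.6.2). Set the unaffected limb to 100, so the affected limb is 120.
- Over-reading by 2% at S2: S2 excess 22.4, baseline (20 + 22.4)/2 = 21.2, outcome 100 × (1 − 0.49 × 20/21.2) = 53.8, a shift of 2.8 points.
- Over-reading by 5% at S2: S2 excess 26, baseline 23, outcome 57.4, a shift of 6.4 points.
- At 40% true excess the same errors give 1.7 and 3.9 points.

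Both errors would pass the 10% check.

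**The case against.** A reader might infer that the biopsy rule means the primary baseline is measured with the arm known. The documents do not support that. S2 puts the measurements and the consistency check before the biopsy, and Section 12.4 builds baseline volume from S1 and S2 only. If allocation falls between the S2 measurements and the biopsy, the primary baseline and the 10% check both precede it. What remains is a possibility left open because the time is not stated and the tape measurer is not said to be blinded. The S3 measurements and the baseline lymphoscintigraphy do follow allocation, but S3 volume is not in the Section 12.4 baseline and the lymphoscintigraphy reader is blinded.

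A reader might also infer that controls will leave because they have nothing to lose. Section 4.3 only lists alternatives; it says nothing about behaviour. Controls also carry a lighter burden: the biopsy is optional, there are no T6 and T7 visits, and the calendar restricts the T5 lymphoscintigraphy to BioBridge recipients. That may favour retention.

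Nor is it settled that the analysis is limited to those operated on, because the Analysis Plan says all assigned. The practical result for someone who leaves before surgery is nevertheless much the same, as step 3 shows. Section 4.2 asks for a final visit after withdrawal, but a visit before surgery yields no surgical outcome.

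The power figures rest on an assumed number of leavers and would be the same for control losses at any time. They show how little slack 12 controls leave, not the effect of early allocation itself.

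Finally, the synopsis has a schema heading whose figure could not be read here. It may show the point of randomization. If so, Sections 3.4 and 12.1.1 should say the same.

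**Conclusion.** The point stands in a limited form. The arm must be known by the S2 biopsy, at least 31 days before surgery, in a trial without masking. Withdrawal before surgery can therefore depend on the arm, and those who withdraw would normally be missing from the primary model under either statement of the analysis set.

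The size is not known. On assumed losses of 2 or 3 of 12 controls and none of 48 intervention participants, power falls from 0.894 to 0.845 or 0.812. On an assumed difference of 0.5 to 1 SD between leavers and the arm mean, the control mean moves by 1.9 to 6.3 points. Arm-dependent baseline volume is a conditional risk, not a consequence of the rule. The change is cheap and worth making; nothing here shows that the comparison is already biased.

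**What to change.** 1. State in Section 3.4 that the S1 to S3 measurements and the final eligibility decision are recorded and locked before the allocation is opened, and that it is opened after S3, as close to surgery as device ordering allows. Section 5.2 has the device ordered for each subject and gives no lead time, so the sponsor should confirm what is feasible.
2. Put the baseline biopsy on the same terms for all participants, in Sections 4, 8.1.1, 9 and 10.3.4.3, so that S2 no longer depends on the arm.
3. Reconcile the analysis sets in Section 12.4 and say how a participant who leaves before surgery is handled.
4. Report withdrawals between randomization and surgery by arm, with reasons.

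The cost is mainly protocol wording. If the biopsy becomes optional for everyone, some intervention participants may decline it. That reduces data for the exploratory histology endpoint, which Section 10.3.4 defines in the intervention group. The change also reduces the exposure without removing it: opening the allocation on the day of S3 still leaves 21 of the 31 days before the earliest surgery, and only a later opening shortens that further.
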